Anemia and transfusion are independent predictors of morbidity and mortality in this patient population. Preoperative anemia is the single most important predictor of perioperative erythrocyte transfusion.⁸ Karkouti et al. demonstrated that approximately 80% of patients with preoperative anemia received at least one erythrocyte transfusions while undergoing cardiac surgery.³ While open cardiac surgeries represent only 1% of the 48 million in-patient surgeries performed annually in the U.S., this small population of patients consumes over 20% of the red blood cell supply in U.S. blood banks.^{3,9} Of those transfused, over 50% receive ≤ 3 units of red blood cells.¹⁰ Whereas transmission of infectious disease has been a historic concern, we now realize that adverse outcomes are more commonly the result of immunomodulation, hypoxia, and free radical induced injury.^{11,12} Studies have repeatedly demonstrated that even low-volume erythrocyte transfusions (1-3 units) can significantly increase the risk of acute renal injury, infection, and pulmonary dysfunction following cardiac surgery.^{1-3,8,9} Reduction and possible elimination of RBC transfusion is now recognized as one of the most significant *modifiable* risk factors leading to these adverse events.

The mechanism of injury in patients with preoperative anemia is either the duration/intensity of the anemia exposure (and resultant organ ischemia) or the harmful effects of erythrocyte transfusion(s) itself. Active preoperative anemia management is a strategy that attempts to minimize both of these events, and in doing so, exert an additive or possibly synergistic effect on improving clinical outcomes. A randomized controlled trial utilizing a standardized transfusion strategy is sorely needed to determine if increases in preoperative hemoglobin lead to improved outcomes. Conducting a feasibility propensity-matched study is an essential step for insuring the adequacy of future trials designed to answer this important question.

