- *Specific Aim 2:* To determine the adherence of patients and health care team to the procedures included in the study protocol (scheduled appointments, surveillance and transfusion strategies).
- *Specific Aim 3:* To determine the increase in hemoglobin levels and reticulocyte count following a

short-course of EPO plus supplemental IV iron vs. standard of care management in matched patients scheduled for CABG, valve, or CABG/valve surgery.

- *Specific Aim 4:* To assess differences in the proportion of patients receiving erythrocyte transfusions and number of blood products utilized (RBC, platelets and plasma) in the peri- and post-operative periods for those receiving a short-course of EPO plus supplemental IV iron vs. standard of care management in matched patients scheduled for CABG, valve, or CABG/valve surgery.
- *Specific Aim 5:* To determine the frequency and intensity of pre-defined clinical outcomes (mortality, major cardiac, renal, neurological events [associated with anemia] and infection) in those receiving a short-course of EPO plus supplemental IV iron vs. standard of care management in matched patients scheduled for CABG, valve, or CABG/valve surgery.

II. BACKGROUND:

Active preoperative anemia management is *not* currently the standard of care at our institution. Cost associated with erythrocyte transfusions at UT Southwestern University Hospitals exceeds \$20M dollars annually. This figure does not include costs associated with treatment of known complications of red blood cells transfusions (renal insufficiency, respiratory failure, infection and prolonged length of stay, etc).¹⁹⁻²⁰ Fifty percent (50%) of our cardiac surgical population suffers from preoperative anemia and seventy-nine (79%) of these patients will receive one or more erythrocyte transfusions. In contrast, the incidence of erythrocyte transfusion was only 35% in those *without* preoperative anemia in CY2011-12.

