Propensity score matching (PSM) is a statistical matching technique that attempts to estimate the effect of a treatment or other intervention by accounting for the covariates that predict receiving the treatment. PSM attempts to reduce the bias due to confounding variables that could be found in an estimate of the treatment effect obtained from simply comparing outcomes among units that received the treatment versus those that did not. This feasibility propensity-matched study is being conducted to guide the design of a future randomized, controlled trial (RCT) that examines the effects of active preoperative anemia management on erythrocyte transfusion and clinical outcomes. The RCT will test the hypothesis that a *short*-course (1-4 weeks) of EPO plus IV iron is superior to the standard of care at reducing erythrocyte transfusion and improving outcomes in *anemic* patients scheduled for cardiac surgery. Means and standard deviations derived from pilot data on changes in hemoglobin levels, reticulocyte count and differences in erythrocyte transfusion and clinical outcomes will be analyzed for possible use in sample size calculations for the larger RCT. This study will also provide valuable information in determining whether the addition of other clinical sites with similar patient populations will be needed in order to help recruit patients for timely completion of the RCT. In addition, the study will provide important information on issues related to data collection, data management, adherence to the study protocol, transfusion and surveillance strategies and classification of clinical outcomes and adverse events.

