Anemic patients scheduled to undergo CABG, valve, or CABG/valve surgeries will be considered for the study. Patients who fulfill all the inclusion/exclusion criteria will be asked to participate in the study. The proportion of screen failures and eligible patients who refuse to participate will be recorded using a screen failure log. Patients who agree to be in the study and sign an informed consent form will be sequentially enrolled into the treatment group. The treatment group will receive up to three doses of EPO 300U/kg. The first dose of study medication will be administered up to 28 days before the day of surgery and the second will be administered 1-7 days before the day of surgery. These first two doses will be given at least 7 days apart. A third dose may be administered two to four days following surgery. All 3 doses will be administered subcutaneously and per surveillance strategy guidelines. In addition, supplementation

with IV iron (feraheme; 510mg delivered per IV infusion over a minimum of 15 minutes) will be given following the first two preoperative doses of EPO.

Differences in hemoglobin levels and reticulocyte counts from baseline to the day of surgery (preop to POD#0) and postoperative day five (POD#5), proportion of patients receiving erythrocyte transfusions and number of blood products (RBC, platelets and plasma) utilized and pre-defined clinical events (mortality, major cardiac, renal, neurological events [associated with anemia] and infection) will be assessed in all treated participants. Each patient will be enrolled in the study up to 28 days before the day of surgery and for up to 30 days following the day of surgery. This feasibility propensity-matched study will sequentially enroll 23 more treatment subjects to total 25. The propensity-matching control group will be comprised of 25 total “like” patients for comparison. The source of the data for the control group will be the Society of Thoracic Surgery (STS) Database, an institutional registry.

Study medications:

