The analysis of this feasibility study will be mainly descriptive and will focus on confidence interval estimation. Results from hypothesis testing will be treated as preliminary and interpreted with caution, as no formal power calculations have been carried out.

Analyses will be performed using parametric and nonparametric univariate and multivariate (where appropriate) statistical methods. Univariate distribution of all variables will initially be performed assessing their distribution with the use of scatter plots and histograms. These results will be used as guidelines in the application of both univariate and multivariate techniques. For descriptive purposes, continuous variables with normal distribution will be described using means, variance and standard deviations; otherwise, medians, interquartile and full ranges will be used. For variables showing distributions that are significantly away from normality, nonparametric statistical tests will be applied. Differences will be considered significant when $P < .05$.

Dichotomous variables will be presented as percentages and analyzed using chi-square or Fisher's exact tests as appropriate. Student t tests or Mann-Whitney U tests will be used to assess differences between independent continuous variables. The analysis of paired continuous variables (such as changes of hemoglobin level or reticulocyte counts from baseline to the day of surgery) will be performed with paired student t tests or Wilcoxon signed rank tests for normally or non-normally distributed variables, respectively. Multivariable regression techniques, including linear mixed models, will be used to analyze differences in continuous variables measured at several different points during the study between the groups (such as hemoglobin level, reticulocyte count, creatinine, etc.) accounting for the within-subject correlation of the data. All statistical analyses will be performed with SAS® software (Version # 9.3, SAS Institute Inc. Cary, NC).

References

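### The proportion transfused has no planned adjustment for baseline hemoglobin, and no post-match balance on hemoglobin is stated

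*Combined protocol and SAP*

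**What the plan says.** Under Research Design and Methods (Section III), 25 treated patients are enrolled one after another. The plan adds: "The propensity-matching control group will be comprised of 25 total" similar patients, and "The source of the data for the control group will be the Society of Thoracic Surgery (STS) Database". Matching is described in general terms, as "accounting for the covariates that predict receiving the treatment". The covariates are not listed, and no balance check after matching is described.

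Clinical Outcomes makes the proportion transfused a secondary outcome. The primary objective is enrollment and adherence.

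The Biostatistics section (XIII) opens: "The analysis of this feasibility study will be mainly descriptive and will focus on confidence interval estimation". It then says: "Dichotomous variables will be presented as percentages and analyzed using chi-square or" Fisher's exact tests. Regression is named for another kind of outcome: "Multivariable regression techniques, including linear mixed models, will be used to analyze differences in continuous variables measured at several different points during the study". One general sentence allows multivariate methods where suitable but names no outcome, model or covariate.

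On the importance of Hb, the opening section says: "Preoperative anemia is the single most important predictor of perioperative erythrocyte transfusion". Background gives 79% transfused among the institution's anemic patients, and by contrast "the incidence of erythrocyte transfusion was only 35% in those" without anemia.

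**The concern.** The groups are not randomized, so any difference in baseline Hb between them carries over into the transfusion comparison. By the protocol's own account Hb status is the leading predictor of transfusion, and the Transfusion Strategy section ties transfusion to Hb levels. The match is the only stated control. Matching on a score does not guarantee balance on each variable in it, least of all with 25 pairs.

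What is at stake is the estimated transfusion difference and its confidence interval. Interval estimation is the declared focus of the analysis. Clinical Outcomes says the data will feed the power analysis of the larger randomized trial, and Research Design and Methods lists transfusion differences for possible use there.

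**Working it through.** The plan gives no power, target effect or derivation of 25 per group, so there is no figure to reproduce. The check is how far a leftover Hb gap would move the unadjusted difference.

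**Inputs from the documents.** 25 v 25; 79% transfused with anemia, 35% without.

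**Assumptions (not in the documents).** Hb SD 1 g/dL; control risk 79%; treated risk 79% (no effect) or 50%; anemic and non-anemic patients 2 to 3.5 g/dL apart on average.

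**1. Slope.** ln(0.79/0.21) − ln(0.35/0.65) = 1.325 + 0.619 = 1.944. Divided by 3.5 and by 2, this is 0.56 and 0.97 in log-odds per g/dL. It is borrowed from the crude contrast because no slope within anemic patients is given. Slopes of 0.25 and 0 are therefore also tried.

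**2. Shift of the unadjusted difference.** With gap d in SD units and slope b, the group's risk is p(d) = ∫ 1/(1 + exp(−(a − b(x + d)))) φ(x) dx, where a is set so that p(0) is the assumed risk. The shift is |p(d) − p(0)|, in percentage points over both directions:

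| Slope b | Risk | Gap 0.25 SD | Gap 0.5 SD |
|---|---|---|---|
| 0.56 | 79% | 2.1–2.3 | 4.1–4.7 |
| 0.56 | 50% | 3.2 | 6.4 |
| 0.97 | 79% | 3.3–3.7 | 6.2–7.8 |
| 0.97 | 50% | 5.0 | 10.0 |
| 0.25 | 79% | 1.0 | 2.0–2.1 |
| 0.25 | 50% | 1.5 | 3.1 |
| 0 | either | 0 | 0 |

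**3. Effect of adjusting.** Simulation used 20,000 studies per scenario, a linear model on group with or without baseline Hb, HC2 robust errors and the same t cut-off (24 df) for both. For slopes 0.56 to 0.97:
- 0.25 SD: shift 2–5 points unadjusted, at most 1 adjusted; coverage of the 95% interval 93%–96% v 95%–96%.
- 0.5 SD: shift 4–10 points unadjusted, at most 2 adjusted; coverage 88%–96% v 95%–96%.
- Width, adjusted relative to unadjusted: 1%–7% narrower when Hb is balanced. The largest penalty is about 5% wider at 0.5 SD.

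If Hb has no effect, the adjusted interval is up to 1% wider when Hb is balanced and 3%–4% wider at 0.5 SD.

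**4. Sampling error for scale.** The half-width is 1.96 × √(p1q1/25 + p2q2/25): 22.6 points at 79% v 79%, and 25.3 at 79% v 50%. With the t cut-off (2.064) and the HC2 factor √(25/24), these become 24.3 and 27.2. The overall range is 22 to 28 points.

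**5. Gaps arising by chance.** With within-pair Hb correlation c, the standardized difference has SD √(2(1 − c)/25) = 0.237, 0.200 and 0.126 at c = 0.3, 0.5 and 0.8. A gap above 0.25 SD then has probability 0.29, 0.21 and 0.05; above 0.5 SD, 0.035, 0.012 and below 0.0001. Chance gaps do not harm coverage averaged over studies. The concern is a gap that the match itself leaves.

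**6. Sizing the larger trial.** n per arm = (1.96√(2p̄q̄) + 1.282√(p1q1 + p2q2))²/(p1 − p2)². For 79% v 50% at 90% power this gives 56. Moving the second risk by 2 points gives 49 or 64, and by 5 points 41 or 79. Moving it by one standard error of the pilot difference (12.9 points) gives 28 or 165.

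**The case against.** The strongest reply is that Hb is already handled by the design. The protocol defines matching as covering variables that predict treatment. Hb determines entry (Section VI) and governs preoperative dosing (Surveillance Strategy), so by that definition it plausibly belongs in the score. This stands. The unlisted covariates are missing detail, and a reader who infers that the comparison is uncontrolled for Hb goes too far. What remains is that balance is neither promised nor checked, and no adjustment is planned if it fails.

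The general multivariate sentence does permit adjustment, but permission is not a plan.

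It is also fair that the gap is assumed and the gain can be small. At 0.25 SD with slope 0.56 or less, root mean squared error changes by less than half a point either way, and adjusting is slightly worse at slopes 0.25 and 0. A clear gain, about 2 to 3 points, appears at slope 0.97 with a 0.5 SD gap.

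Four further inferences are tempting and not supported:
- **That controls may be non-anemic.** The Hb limit is written for enrolled subjects and not restated for controls, but the controls are described as similar matched patients, and nothing says non-anemic ones would be used.
- **That a reader could not tell which way the result is shifted.** Baseline Hb is needed in both groups for the change outcome. If it is shown by group, the direction of any gap is visible.
- **That the larger trial would be mis-sized for lack of adjustment.** Step 6 shows sampling error dominates, with or without it.
- **That the Hb comparison has the same defect.** Mixed models are named for Hb between groups.

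**Conclusion.** The concern holds in a limited form. The only method named for the between-group proportion transfused is an unadjusted test. No adjustment for baseline Hb is planned, and no balance on it after matching is stated.

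The possible shift is about 2–5 points for a 0.25 SD gap and 4–10 points for a 0.5 SD gap, conditional on the assumed SD, risks and slopes. It is 1–3 points at a slope of 0.25 and nil at 0. The documents do not show that a gap will exist. Beside a half-width of 22–28 points the effect is modest. Tests are already labeled preliminary, and the primary objective is unaffected. The change is worth making because it is cheap and removes most of an avoidable bias in a reported estimate. It will not make this pilot precise enough to size a trial.

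**What to change.** In the Biostatistics section, add the transfusion risk difference with a 95% CI adjusted for pre-treatment baseline Hb, for example from a regression on group and baseline Hb with robust standard errors. Keep the planned chi-square or Fisher result beside it. Use the value from before any study drug, not day-of-surgery Hb, which treatment is meant to change. Show baseline Hb by group with its standardized difference after matching. State that sampling error dominates any sample size derived from this pilot.

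The text change is a few sentences, and Clinical Outcomes already needs baseline Hb in both groups. The real work is timing. Treated patients have their baseline visit 7 to 28 days before surgery, while no section says when the registry Hb was measured, so a common definition is needed. Beyond slightly more analysis work, the price is an interval up to about 5% wider if Hb is imbalanced by 0.5 SD.

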You have agreed to participate in a research study testing whether it is practical to treat preoperative anemia up to 30 days prior to cardiac surgery. We think that treating anemia prior to cardiac surgery will result in better outcomes, but before we can conduct a study big enough to test that idea we first need to perform a smaller study to see whether our approach is feasible. We are interested in obtaining feedback about how important the treatment of preoperative anemia is to you. Answering the following questions will help physicians and hospitals understand your opinion of the approach being taken by this study.

A. Strongly Agree B. Agree C. Neutral D. Disagree E. Strongly disagree

- 1) I have concerns about receiving a blood transfusion.
A B C D E

- 2) I would be willing to receive subcutaneous and intravenous injections preoperatively (to treat my anemia) if it could save me 1-2 units of red blood cell transfusions during or after my surgery.
A B C D E

- 3) If it was considered to be medically safe by my cardiologist and surgeon, I would be willing to schedule my surgery up to 30 days after the decision to have surgery was made if this would decrease my chance of receiving a blood transfusion.
A B C D E

- 4) I would be willing to make 1-2 additional trips to UT Southwestern in order to receive treatment for my anemia.
A B C D E

- 5) The fact that UT Southwestern physicians are concerned about decreasing my chance of receiving blood transfusion(s) is important to me.
A B C D E

- 6) Knowing a hospital is committed to treating my anemia preoperatively to avoid blood transfusion(s) could influence my selection where to have my surgery performed.
A B C D E
